2.6 Analysis of secondary objectives

2.6.1 Efficacy endpoints

All following secondary efficacy variables will be analyzed using the FAS, PP set and subset of patients in FAS who had 3-step titration

2.6.1.1 MMSE score at Week 8

The change from baseline to Week 8 in MMSE total score will be summarized descriptively and analyzed using the same MMRM model used for the primary analysis. The estimated mean change along with two-sided 95% confidence interval will be presented.

Same figure will present the estimates and 95% confidence intervals of change from baseline in MMSE score at both Week 8 and Week 24.

2.6.2 Safety analyses

All safety variables will be reported using the safety set.

In addition, the adverse events, serious adverse events and adverse events of special interest summaries described in the following sub-sections will also be presented by the safety subgroups specified in [Section 2.2.1.2](#).

2.6.2.1 Adverse events (AEs)

All adverse events starting on or after the first treatment will be included in all summaries and will also be listed. Adverse events occurring after signing of the informed consent prior to the start of study treatment will be listed only.

These adverse events will also be summarized by overall, by study periods as Week 1 to Week 4, Week 4 to Week 8, Week 8 to Week 12, Week 12 to Week 16, Week 16 to Week 20 and Week 20 to Week 24 by the following variables.

Adverse events by SOC and PT

All adverse events starting on or after the first treatment will be coded utilizing the MedDRA dictionary, tabulated, and analyzed by primary system organ class and preferred term.

Primary system organ classes will be sorted alphabetically and, within each primary system organ class, the preferred terms will be sorted in descending order of frequency.

If a patient reported more than one adverse event with the same preferred term, the adverse event will be counted only once. If a patient reported more than one adverse event within the

same primary system organ class, the patient will be counted only once at the system organ class level.

AEs by severity

All adverse events will be summarized by maximum severity, primary system organ class and preferred term. If a patient reports more than one adverse event within the same primary system organ class, only one adverse event will be counted for that patient at the highest severity level in the total row for each primary system organ class. If a patient reported more than one adverse event with the same preferred term, the highest (maximum) severity will be presented. Missing severity will be assumed to be severe in the summary table.

AEs suspected to be related to study drug

The treatment emergent adverse events suspected to be related to study drug (according to the investigators) will be summarized by primary system organ class and preferred term. Relationship to study drug is considered as suspected for those events where "Relationship to study drug" is answered by the investigator as "Suspected".

AEs leading to permanent study drug discontinuation

Treatment emergent adverse events leading to permanent study drug discontinuation, regardless of study drug relationship, will be summarized by primary system organ class and preferred term.

AEs requiring dose adjustment or interruption

Treatment emergent adverse events requiring dose adjustment or interruption, regardless of study drug relationship, will be summarized by primary system organ class and preferred term.

2.6.2.2 Serious adverse events (SAE)

Number and percentage of patients with serious adverse events, regardless of study drug relationship, will be presented by primary system organ class and preferred term. These SAEs will also be summarized by overall, by study periods as Week 1 to Week 4, Week 4 to Week 8, Week 8 to Week 12, Week 12 to Week 16, Week 16 to Week 20 and Week 20 to Week 24.

Additionally separate tables will be provided for SAEs occurring more than 30 days after the last treatment administration for patients who discontinued the study treatment but remained in the study for more than 30 days and for SAEs which happened between Visit 1 (screening) and the time of first treatment for all patients in the safety set.

SAEs will also be listed separately.

2.6.2.3 Adverse events of special interest / grouping of AEs

The adverse events of special interest (Gastrointestinal events and skin events) will be summarized separately for the safety set by overall and chronologically by study periods as Week 1 to Week 4, Week 4 to Week 8, Week 8 to Week 12, Week 12 to Week 16, Week 16 to Week 20 and Week 20 to Week 24. A listing of such AEs will also be presented including action taken and outcome.

AEs of special interest are defined as the following terms. These will be taken from the latest MedDRA dictionary at the time of database lock.

GI event (“Gastrointestinal symptoms”)

- HLT “Diarrhoea (excl infective)”
- HLT “Nausea and vomiting symptoms”

Skin event (“Application site skin reactions and irritations”)

- HLT “Application and instillation site reactions”
- PT “Dermatitis allergic”
- PT “Dermatitis contact”
- PT “Administration site reaction”
- PT “Administration site pain”
- PT “Administration site infection”

2.6.2.4 Deaths

All the deaths in the clinical database will be listed with the investigator-reported principal cause. Deaths occurring after the first administration of study treatment until 30 days after the date of last treatment will be summarized with numbers and percentages.

2.7 Other safety data

2.7.1 Laboratory data

Laboratory measurements will include Hematology (Erythrocyte count, leukocyte count, hemoglobin, hematocrit, platelet count); Blood chemistry (Total protein, uric acid, ALP, AST, ALT, LDH, cholinesterase, blood urea nitrogen, creatinine, Na, K, Cl, total cholesterol, triglycerides, CPK, albumin, Ca, P, total bilirubin, amylase) and Urinalysis (Glucose, protein, occult blood).

All data will be converted into SI units (except Cholinesterase, which will be reported as collected (in U/L)) listed for the safety set with abnormal values flagged. A listing of all patients in the safety set will be provided.

The change from baseline at Week 24 is provided for Hematology and Chemistry. For urinalysis, descriptive statistics is provided for baseline and Week 24.

Liver function tests

The metabolism of a drug can have an impact on the safety profile of the drug. To evaluate potential drug-induced liver injury, the patients with newly occurring or worsening abnormalities in liver function tests at any time post-baseline will be listed based on the following criteria:

Notable Liver events:

	Definition/ threshold
LIVER EVENTS	
 • ALT or AST $> 5 \times$ ULN • ALP $> 2 \times$ ULN (in the absence of known bone pathology) • TBL $> 2 \times$ ULN (in the absence of known Gilbert syndrome) • ALT or AST $> 3 \times$ ULN and INR > 1.5 • Potential Hy's Law cases (defined as ALT or AST $> 3 \times$ ULN and TBL $> 2 \times$ ULN [mainly conjugated fraction] without notable increase in ALP to $> 2 \times$ ULN) • Any clinical event of jaundice (or equivalent term) • ALT or AST $> 3 \times$ ULN accompanied by (general) malaise, fatigue, abdominal pain, nausea, or vomiting, or rash with eosinophilia • Any adverse event potentially indicative of a liver toxicity*

*These events cover the following: hepatic failure, fibrosis and cirrhosis, and other liver damage-related conditions; the non-infectious hepatitis; the benign, malignant and unspecified liver neoplasms

TBL: total bilirubin; ULN: upper limit of normal

2.7.2 Vital signs

Vital signs measurements include systolic and diastolic blood pressure (SBP and DBP), pulse rate, and body weight. The following summaries will be presented for the safety set:

2.7.2.1.1 Summary of absolute values and change from baseline

Vital signs including the changes from baseline will be summarized at the scheduled visits and time points. The maximum and minimum post-baseline SBP, DBP, and pulse rate values will also be summarized including the respective changes from baseline.

Body weight will be summarized by scheduled visits.

2.7.2.1.2 Notable absolute values and change from baseline

The number and percentage of patients with newly occurring or worsening notable values, including notable change from baseline, will be summarized by vital sign parameter and post-baseline visit. An additional section will be included for abnormalities occurring at any time point over the treatment period, considering all post-baseline data from scheduled, unscheduled and premature discontinuation visits. Notable absolute values and notable changes from baseline for each vital sign parameter are defined as:

Table 2-1 FDA (DNDP) Criteria: Clinically Notable Vital Signs Abnormalities

Variable			Change Relative to Baseline
Pulse Rate	> 120 bpm	And an	Increase of ≥ 15 bpm
	< 50 bpm	And a	Decrease of ≥ 15 bpm
Systolic BP	> 180 mmHg	And an	Increase of ≥ 20 mmHg
	< 90 mmHg	And a	Decrease of ≥ 20 mmHg
Diastolic BP	> 105 mmHg	And an	Increase of ≥ 15 mmHg
	< 50 mmHg	And a	Decrease of ≥ 15 mmHg

Weight	Increase of >= 7%
	Decrease of >= 7%

A listing of all patients with notable vital sign values and changes will be provided for the safety set.

2.7.3 ECG

ECG measurements include heart rate, QT interval, RR interval, PR interval, QRS duration, QTcF and QTcB, taken in a supine position after rest will be summarize descriptively for safety set. Listing will be provided for all patients.

2.8 Patient-reported outcomes

The following secondary endpoint related to patient reported outcome will be analyzed:

2.8.1.1 QOL-AD score

The QOL-AD is a brief, 13-item measure designed to obtain a rating of the patient's Quality of Life from the caregiver. A lower score indicates more severe impairment.

The change from baseline at Week 24 in the QOL-AD total and sub-item scores (by patients or caregivers) will be summarized along with 95% confidence interval of the mean for the FAS. Assessment of QOL of a given patient by his/her caregiver should be considered as primary measurement while assessment of QOL of a given patient by his/herself will be recorded as reference.

In addition, association between QOL-AD total score and each of MMSE total score, NPI-10 total score, J-CGIC and Modified Crichton Scale total score will be explored. A logistic regression will be considered to select the appropriate factors and thereafter to test whether or not the selected factors are associated with QOL-AD.

Similarly, the association between QOL-AD and number of gastrointestinal AEs and Application skin AEs will be explored using a regression analyses.

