1.2 Study objectives and endpoints

Objectives	Endpoint Title, Description and Reporting Time Frame for analysis and Unit of Measure	Protocol Statistical Analysis Section
Primary		
To evaluate the efficacy of rivastigmine patch with 1-step titration on cognitive function measured as change from baseline to week 24 in the total score of MMSE in mild to moderate AD patients who failed to benefit from other cholinesterase inhibitors (ChEIs)	Endpoint Title: Change from baseline to week 24 in the total score of MMSE Time Frame : Up to week 24	Appendix 16.1.1-Protocol-Section 9.4
Secondary		
To evaluate the safety, tolerability of Exelon® patch with 1-step titration for up to 24 weeks.	Endpoint Title: Monitoring and recording of all adverse events (AEs) and serious adverse events (SAEs). Time Frame: Up to week 24.	Appendix 16.1.1-Protocol-Section 9.5

Objectives	Endpoint Title, Description and Reporting Time Frame for analysis and Unit of Measure	Protocol Statistical Analysis Section
To evaluate the efficacy of Exelon® patch with 1-step titration measured as the MMSE score at week 8.	Endpoint Title: Change from baseline to Week 8 in MMSE total score. Time Frame : Week 8	
To evaluate the efficacy of Exelon® patch with 1-step titration measured as the NPI-10 score at week 8 and week 24.	Endpoint Title: Change in NPI-10 score from baseline to week 8 and week 24 Time Frame : Week 8 and Week 24	
To evaluate the efficacy of Exelon® patch with 1-step titration measured as QOL-AD score at week 24.	Endpoint Title: Change in QOL-AD score from baseline to week 24 Time Frame : Week 24	Appendix 16.1.1-Protocol-Section 9.5
To evaluate the efficacy of Exelon® patch with 1-step titration measured as the J-CGIC score at week 4, week 8, week 16, and week 24.	Endpoint Title: Change in J-CGIC score from baseline to week 4, 8, 16 and 24 Time Frame : Week 4, 8, 16, 24	
To evaluate the efficacy of Exelon® patch with 1-step titration measured as Modified Crichton Scale score week 4, week 8, week 16, and week 24.	Endpoint Title: Change in as Modified Crichton Scale score from baseline to week 4, 8, 16 and 24 Time Frame : Week 4, 8, 16, 24	
To evaluate the formulation usability of Exelon® patch for up to 24 weeks as measured by the formulation usability questionnaire answered by caregiver.	Endpoint Title: Formulation usability score up to week 24 Time Frame : Up to week 24	

2 Statistical methods

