2.10.1.1 J-CGIC

J-CGIC is a global assessment scale to assess change of the patient's clinical symptoms, which are assessed subjectively by clinicians with seven grades. (1: Marked improvement, 2: Moderate improvement, 3: Mild improvement, 4: Unchanged, 5: Mild Worsening, 6: Moderated Worsening, 7: Marked Worsening). The number and percentage of patients in each grade will be displayed at visits 3, 4, 6 and 8. Also, proportion and 95% confidence interval for the proportions of the patients without worsening (1: Marked improvement, 2: Moderate improvement, 3: Mild improvement, 4: Unchanged) and with improvement (1: Marked improvement, 2: Moderate improvement, 3: Mild improvement) will also be provided.

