5.3.4 Regression Model

Regression Model: QOL-AD total score = MMSE total score + NPI-10 score + J-CGIC grade + Modified Crichton total score.

Use SAS code:

```
proc reg data = xxxx;  
model QOL-AD total score = MMSE total score NPI-10 score J-CGIC grade Modified  
Crichton total score / selection = forward slentry = 0.95;  
run;
```

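### The exploratory QOL-AD regressions name no visit and contain no baseline QOL-AD term, so prior quality of life can confound the adverse-event association

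*SAP*

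**What the plan says.** The QOL-AD endpoint in SAP 1.2 is "Change in QOL-AD score from baseline to week 24". SAP 2.8.1.1 summarises it that way, with a 95% confidence interval, and makes the caregiver's rating the main measurement.

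The same section then adds two exploratory analyses.

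- **Scale scores.** The "association between QOL-AD total score and each of MMSE total score, NPI-10 total score, J-CGIC and Modified Crichton Scale total score will be explored", followed by a test of the factors that are selected. SAP 5.3.4 writes the model as "Regression Model: QOL-AD total score = MMSE total score + NPI-10 score + J-CGIC grade + Modified Crichton total score".
- **Adverse events.** Similarly, "the association between QOL-AD and number of gastrointestinal AEs and Application skin AEs will be explored using a regression analyses". No code or model statement for this regression appears elsewhere in the SAP.

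Neither analysis is given a visit, a baseline QOL-AD term or a choice between caregiver and patient rating. Protocol Table 6-1 and section 6.4.4 schedule QOL-AD at Visits 2 and 8 only. On J-CGIC, SAP 2.10.1.1 states that "J-CGIC is a global assessment scale to assess change of the" patient's symptoms, in seven grades, displayed at Visits 3, 4, 6 and 8.

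**The concern.** The trial has one arm, so no randomised comparison balances patients who differ at entry. A regression on quality of life under the patch therefore relies on covariates to separate what happened during treatment from what was there before. The obvious covariate, baseline QOL-AD, is collected but is not in the written model.

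This matters most for the AE regression, because AEs arise after baseline. Suppose patients with poorer quality of life on their previous drug also report more skin or gastrointestinal events. An unadjusted Week 24 analysis would then show an association even if the events did nothing to quality of life. It could be read as a quality-of-life cost of patch reactions.

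The four-predictor model has a second, different difficulty. A change rating stands beside three level scores, with a level as the outcome. If J-CGIC tracks change in quality of life, a level outcome will show less of that link.

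**Working it through.** **1. Which visit can be used.** QOL-AD exists at Visits 2 and 8. J-CGIC exists at Visits 3, 4, 6 and 8 in Table 6-1 and in the SAP. The only scheduled visit common to both is Visit 8 (Week 24). There are two qualifications:

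- Protocol 6.4.3 also lists J-CGIC at Visit 2, against Table 6-1. No on-treatment change could be rated at that visit.
- SAP section 4, point 3, re-maps discontinuation records to the nearest planned visit.

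For the AE regression, which does not contain J-CGIC, the visit is simply not stated.

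**2. Sample size for the checks.** The regressions carry no figure of their own. The plan's evaluable number comes from MMSE precision: (1.96 × 3.0 / 0.6)² = 96.04, rounded up to 97. This reproduces, and n = 97 is used below.

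**3. AE regression at Week 24 without baseline, true AE effect zero.** Let r be the correlation of baseline with Week 24 QOL-AD, and a the correlation of AE count with baseline QOL-AD. Both are assumptions. With no AE effect, the expected correlation of AE count with Week 24 QOL-AD is ρ = r × a. By Fisher's approximation m = atanh(|ρ|) × √(97 − 3), and the rejection rate at the 5% level is Φ(m − 1.96) + Φ(−m − 1.96). For r = 0.7:

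| a | ρ | m | Approximation | Simulation, unadjusted | Simulation, baseline added |
|---|---|---|---|---|---|
| 0 | 0 | 0 | 5.0% | about 5% | about 5% |
| −0.1 | −0.07 | 0.68 | 10.4% | 11% | about 5% |
| −0.2 | −0.14 | 1.37 | 27.7% | 27% | about 5% |
| −0.3 | −0.21 | 2.07 | 54.3% | 55% | about 5% |

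The simulation used 4,000 trials per cell. For a = −0.1, −0.2 and −0.3, the unadjusted rates are 8%, 16% and 32% at r = 0.5, and 13%, 36% and 67% at r = 0.8.

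**4. Precision.** Adjusting for baseline multiplies the residual SD by √(1 − r²), a reduction of 13%, 29% and 40% for r = 0.5, 0.7 and 0.8.

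**5. Level scores against QOL-AD level.** A separate simulation paired Week 24 MMSE with Week 24 QOL-AD, with no association between their changes. It took the SD of MMSE change as 3.0 (SAP section 3) and assumed a baseline MMSE SD of 3.5 and QOL-AD baseline/change SDs of 6/4, 5/5 or 6/3.

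| Baseline correlation | p<0.05, levels only | p<0.05, baseline QOL-AD added |
|---|---|---|
| 0 | 5–6% | 4–6% |
| 0.2 | 17–26% | 4–6% |
| 0.3 | 35–53% | 4–6% |
| 0.4 | 56–78% | 4–6% |
| 0.5 | 74–93% | 4–6% |

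The levels-only results are false positives only if the question is about change. As a description of levels at Week 24 they are real associations.

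**6. J-CGIC.** If J-CGIC relates to QOL-AD only through its change, its correlation with the Week 24 level is its correlation with the change times a dilution factor.

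- With change independent of baseline, the factor is SD(change) / √(SD(baseline)² + SD(change)²). It is 0.55 for 6/4, 0.71 for 5/5 and 0.45 for 6/3.
- With equal variances at the two visits, it is √((1 − r)/2), which is 0.50, 0.39 and 0.32 for r = 0.5, 0.7 and 0.8.

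Under either assumption the effect is attenuation.

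**The case against.** The strongest reply is that these analyses are labelled as exploration, serve no listed objective and feed no primary or secondary estimate. Which scores go with QOL-AD at one visit is a legitimate cross-sectional question, and baseline adjustment answers a different one. This stands, and it limits the point to interpretation. It does not remove the point, because the SAP also plans to test the selected factors, and the AE regression invites a reading in terms of effects.

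A reader might infer three stronger things that the documents do not support.

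- **That the SAP prescribes unadjusted Week 24 totals in both regressions.** Week 24 is an inference, sound for the model with J-CGIC. For the AE regression the response form, visit and covariates are unwritten. The figures in step 3 describe one way of filling that gap.
- **That pre-existing differences drive the associations.** They can confound them. The size depends on correlations that appear nowhere in the documents, and at zero correlation there is no inflation. At a = −0.2 and r = 0.7 the spurious correlation is −0.14, about 2% of variance (0.14² = 0.0196).
- **That including J-CGIC causes the confounding.** It appears in only one of the two regressions, and its link is weakened by the level outcome.

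It is also fair to say that SAP 2.8.1.1 and 5.3.4 have a more visible fault. The text says "A logistic regression will be considered to select the appropriate factors", while the code is a linear model with "selection = forward slentry = 0.95". That is a separate matter and should be settled in the same edit.

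**Conclusion.** The concern holds as a gap in specification with a nearly free remedy. The written four-predictor model omits a baseline value that is already collected, and the AE regression is too thinly specified to show whether it would be included. If that regression is run on unadjusted Week 24 QOL-AD, the nominal 5% error rate stays at 5% or rises to about 55% across the assumed AE–baseline correlations of 0 to −0.3 at r = 0.7. Baseline adjustment returns it to about 5% throughout and also reduces residual variation. These rates rest on 97 analysable patients, approximate normality and the assumed correlations.

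The severity is minor. The planned QOL-AD change summary and the MMSE analyses are unaffected.

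**What to change.** In SAP 2.8.1.1 and 5.3.4:

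1. State Week 24 caregiver QOL-AD as the response in both regressions, and say how re-mapped discontinuation records are treated.
2. Force baseline caregiver QOL-AD into both models, outside the forward selection.
3. Write out the AE model: Week 24 QOL-AD = baseline QOL-AD + number of gastrointestinal AEs + number of application-site skin AEs, counting only events with onset before the QOL-AD date.
4. Optionally, enter changes from baseline in MMSE, NPI-10 and Modified Crichton beside J-CGIC. This alters the question, so it is a choice to be justified. If a cross-sectional description is what is wanted, say so and do not interpret it as an effect of treatment or of AEs.

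The cost is a few lines of SAP text and code and one degree of freedom per model. Patients without a baseline QOL-AD drop out, since the Visit 1 fallback in SAP 2.1.1.3 does not extend to QOL-AD. One gap remains: QOL-AD is optional (Table 6-1) or not done (protocol 6.4.4) at discontinuation for an AE. The AE model will therefore still lack some of the patients most affected by AEs, and the report should say so.

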2.9 Caregiver-reported outcomes

The following secondary endpoints related to caregiver reported outcomes will be analyzed:

2.9.1.1 Neuropsychiatric Inventory (NPI) score

The neuropsychiatric symptoms will be assessed by the 10-item Neuropsychiatric Inventory (NPI). The NPI-10 total score is a sum of the 10 domains, where the score for a domain is defined as the product of frequency (range: 1-4) and severity (range: 1-3). Each domain has a maximum score of 12 and all domains are equally weighted for the total score (thus the range for the total score is 0 to 120). The NPI-10 total score and individual domain scores will be summarized descriptively at visits 2, 4 and 8 respectively. For where, N/A or absent has been marked in the crf, value 0 is considered for the same.

For change from baseline in NPI-10 total score at Week 24, summary statistics and 95% CI of the mean change will be derived for FAS.

